### 3.5 DETERMINATION OF SAMPLE SIZE

With a total of 12 subjects and assuming a null hypothesis of an ABR of 12, then if the true ABR for MarzAA is 6 or less, with a one-tailed 2.5% significance level there is near 100% power to demonstrate this using a one sample Poisson test of the null hypothesis. Even if only 6 subjects were available to be pooled for this analysis, the power would still be in excess of 99%. Thus, a sample of 12 subjects is expected to provide sufficient power for the primary endpoint analysis in this study.

Twelve subjects were chosen to increase the size of the safety data set.

If a subject does not complete the study as defined in the protocol (i.e., before receiving study drug for 50 days at the same dose level) another subject will need to be enrolled in replacement.

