### 8.1 PRIMARY EFFICACY ENDPOINT AND ANALYSIS

#### 8.1.1 Primary Efficacy Endpoint

The analysis of the primary endpoint (annualized bleeding rate (ABR) for spontaneous and traumatic bleeds) under the final treated dose of MarzAA for each subject will be based on the one sample test compared to a pre-defined rate assumed for the on-demand therapy. The pre-defined rate is assumed to be 12 bleeds in total (i.e. one bleed per month), defined as the minimum ABR for each subject according to inclusion criterion 2 (defined as the null hypothesis (H0)). The comparison of the actual ABR for MarzAA at the highest dose for an individual will be performed using the one-sample test for a Poisson rate versus the pre-defined margin of 12 (using an exact Poisson regression model in SAS 9.4). A one-tailed 2.5% significance level will be used For the following hypothesis test:

$$H_0: ABR_{\text{MarzAA}} \geq 12 \text{ versus } H_1: ABR_{\text{MarzAA}} < 12.$$

The ITT population will be used for the statistical analysis of the primary efficacy endpoint.

In order to calculate the ABR for subjects who do not have a total of 12 months of follow up, the ABR will be calculated as:

$$(\text{Number of bleeds/number of months on study}) \times 12$$

Note: number of months is calculated as the exposure (in days) at each dose level / 30.5.

Formally, assume that the hypothesis is: H0:  $\lambda = \lambda_0$  vs Ha:  $\lambda < \lambda_0$ . Let n be the number of subjects, we can calculate the critical point Ncrit which is the largest integer meeting

$$\sum_0^{N_{crit}} e^{-n\lambda_0} \frac{(n\lambda_0)^k}{k!} \leq \alpha \quad (1)$$

If the total number of bleeds during the final MarzAA dose for all subjects is less than Ncrit, then the null hypothesis is rejected.

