**Version 2.0**

**Syneos Health #1009647**

## **APPENDIX I EXAMPLE SAS CODE**

**Poisson regression model for primary efficacy endpoint:**

```
PROC GENMOD DATA = bleed;  
MODEL abr = / DIST = poi LINK = log PRED OFFSET = <ln (12)>;  
EXACT intercept/ESTIMATE = parm ONESIDED ALPHA = 0.025;  
RUN;
```

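### SAP 8.1.1 rejects only below N_crit although N_crit itself lies inside the 2.5% rejection region: a conservative off-by-one, material only once equation (1) is put on person-time

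*SAP*

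**What the plan says.** SAP 8.1.1 describes the primary test in two ways.

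- **As an exact test.** The section compares the bleeding rate at the final dose with 12 per year by an exact one-sample Poisson test: "A one-tailed 2.5% significance level will be used For the following hypothesis test". Appendix I codes it with "EXACT intercept/ESTIMATE = parm ONESIDED ALPHA = 0.025". Protocol 9.4.2 likewise asks for an exact p-value at a one-tailed 2.5% level.
- **As a critical value.** Equation (1) sums the null Poisson probabilities from 0 up to and including N_crit, with mean n times the null rate, and N_crit is the count "which is the largest integer meeting" the condition that this sum is at most alpha. The decision sentence then reads "If the total number of bleeds during the final MarzAA dose for all subjects is less than" N_crit, and in that case the null hypothesis is rejected.

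The power statement is in SAP 3.5: "With a total of 12 subjects and assuming a null hypothesis of an ABR of 12", and "if the true ABR for MarzAA is 6 or less, with a one-tailed 2.5% significance level there is near 100% power". For half the sample it says "Even if only 6 subjects were available to be pooled for this analysis, the power would still be in excess of 99"%.

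The SAP does not say which description governs if they differ. Its section 14 records only the change of software for the exact analysis.

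**The concern.** The sum in equation (1) includes N_crit, so N_crit is the last count inside the rejection region and its exact one-sided p-value is at most 0.025 by construction. Requiring the total to be strictly smaller drops that count. For one possible result the SAP therefore gives opposite answers on its primary hypothesis: the exact test rejects and the critical-value rule does not.

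If the total fell there, the conclusion would depend on which sentence was followed, and that choice would be made with the data in view. The strict rule also runs below the stated 2.5% level, so some power could be given away. How much depends on the null mean.

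**Working it through.** **Inputs.** One-sided alpha 0.025 and null ABR 12 (SAP 8.1.1). ABR 6 under the alternative, and 12 or 6 subjects (SAP 3.5). Months counted as days / 30.5 (SAP 8.1.1). Completion requires 50 days at one dose level (SAP 3.5, protocol 4.2).

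**Formulas.** X is the total bleed count, Poisson with mean mu0 under the null and mu1 = mu0 × 6/12 under the alternative.

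- N_crit = largest c with P(X ≤ c | mu0) ≤ 0.025.
- Inclusive rule (reject if X ≤ N_crit): size P(X ≤ N_crit | mu0), power P(X ≤ N_crit | mu1).
- Strict rule as written (reject if X < N_crit): the same with N_crit − 1.

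**Step 1. Reproduce the SAP's power.** Equation (1) uses mu0 = n × 12, which amounts to one year per subject.

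- n = 12: mu0 = 144, mu1 = 72. P(X ≤ 120 | 144) = 0.0227 and P(X ≤ 121 | 144) = 0.0279, so N_crit = 120. Power exceeds 99.999% under both rules.
- n = 6: mu0 = 72, mu1 = 36. P(X ≤ 55 | 72) = 0.0224 and P(X ≤ 56 | 72) = 0.0302, so N_crit = 55. Power is 99.88% inclusive and 99.81% strict.

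Both stated powers reproduce under either rule, so they do not show which one was intended.

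**Step 2. The contradiction at the printed inputs.** With n = 12, a total of 120 has exact p = 0.0227. The exact test rejects and the written rule does not. The strict size is P(X ≤ 119 | 144) = 0.0183. At ABR 6 the chance of landing on 120 is about 6 in 100 million, so nothing practical is lost there. At ABR 9 power is 88.4% against 86.5%.

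**Step 3. The same rules on person-time.** Assume that every subject contributes exactly 50 days.

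- 12 subjects, 30.5-day month: mu0 = 12 × 50/30.5 = 19.67. P(X ≤ 10) = 0.0129 and P(X ≤ 11) = 0.0251, just over the limit, so N_crit = 10.
- 12 subjects, 365.25-day year: mu0 = 12 × 12 × 50/365.25 = 19.71. P(X ≤ 11) = 0.0246 and P(X ≤ 12) = 0.0444, so N_crit = 11.
- 6 subjects, 30.5-day month: mu0 = 6 × 50/30.5 = 9.84. P(X ≤ 3) = 0.0117 and P(X ≤ 4) = 0.0325, so N_crit = 3.

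| Case | mu0 | N_crit | Size, ≤ | Size, < | Power at ABR 6, ≤ | Power at ABR 6, < |
|---|---|---|---|---|---|---|
| 12 subjects, as printed | 144 | 120 | 2.27% | 1.83% | >99.999% | >99.999% |
| 6 subjects, as printed | 72 | 55 | 2.24% | 1.64% | 99.88% | 99.81% |
| 12 × 50 days, 30.5-day month | 19.67 | 10 | 1.29% | 0.60% | 60.4% | 47.9% |
| 12 × 50 days, 365.25-day year | 19.71 | 11 | 2.46% | 1.26% | 71.3% | 60.1% |
| 6 × 50 days, 30.5-day month | 9.84 | 3 | 1.17% | 0.32% | 27.7% | 13.2% |

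The loss on person-time is 12.5, 11.2 and 14.5 points in the last three rows. It varies with the true rate: in the 12-subject, 30.5-day case it is 1.7 points at ABR 3 (98.8% against 97.1%) and 5.3 points at ABR 9 (13.1% against 7.8%).

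**The case against.** The strongest reply is that the slip does no harm on the plan's own terms. At a mean of 144 against 72 power is complete under either wording. If the printed threshold of 120 were applied to 50-day counts, with means of about 10 to 20, both wordings would reject almost surely. The sizeable losses appear only after a person-time mean is substituted that equation (1) does not contain, and the missing exposure term is a separate and larger defect. This stands, and it limits what can be claimed here.

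Three further points stand in part.

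- **Exposure.** Fifty days for everyone is an assumption. The primary analysis uses the ITT set, which takes in anyone dosed, including subjects who stop early and are replaced. The month convention alone moves inclusive power from 60.4% to 71.3%, about as much as the effect in question.
- **The model.** A spontaneous bleed after the fifth dose triggers escalation, and completion at the first three levels requires 50 days without one (protocol 4.2 and 6.1.2.1). Final-dose totals are therefore selected downwards and are not a plain Poisson sample at ABR 6.
- **The exact test.** Since it is also specified, the critical-value paragraph can be read as explanation only. The SAP does not say so, however, and that paragraph contains its only explicit rejection rule.

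A reader might infer that the written rule costs substantial power as it stands, or fails the trial at one of its likeliest outcomes. The documents do not support that: at the printed inputs the disputed count is remote under ABR 6. A reader might also infer a false-positive risk from the critical-value slip. There is none, because the strict rule only shrinks the rejection region.

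**Conclusion.** The decision sentence in SAP 8.1.1 is off by one against its own definition of N_crit, and at that single count it contradicts the exact one-sided 2.5% test. This follows from the text and needs no assumption about exposure.

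The error is conservative. At the printed mean of 144 it lowers the size from 2.27% to 1.83% and leaves power at ABR 6 essentially unchanged. It becomes material only when the null mean is put on actual person-time. Assuming Poisson counts and exactly 50 days for each of 12 subjects, power at ABR 6 is 60% against 48% (30.5-day month) or 71% against 60% (365.25-day year). Part of the shortfall from 2.5% is Poisson discreteness rather than this error: the inclusive rule itself has a size of only 1.29% in the first of those cases.

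This should be fixed, together with the exposure correction to equation (1). Correcting the exposure alone would leave the slip in place where it costs most.

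**What to change.** In SAP 8.1.1, change the decision sentence so that the null hypothesis is rejected when the total is less than or equal to N_crit. Add one sentence saying that the exact one-sided p-value on the total bleed count, at most 0.025, decides the primary hypothesis. Keeping the strict inequality and redefining N_crit as the smallest count whose cumulative null probability exceeds alpha would be equivalent.

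Make the change together with the person-time correction to equation (1), before database lock. Do not simply delete the sentence and leave the Appendix I code as the rule: that code models the annualised rate with offset ln(12) and has no exposure term, so it is not the exact test on the bleed count.

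The cost is one phrase and one sentence in the SAP, with no effect on data or design. Aligning the Appendix I code with the bleed count and exposure is a small programming task that belongs to the person-time correction.

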**Statistical Analysis Plan**

Catalyst Biosciences, Inc. Protocol # MAA-201

Version 2.0

Syneos Health #1009647

In order to compare ABR (spontaneous and total) during part 2 when on final MarzAA dose level with the actually recorded historical data, a Poisson regression model using PROC GENMOD procedure will be used with the ABR as the dependent variable, intercept as the independent variable and log e transformed of 12 will be used as offset variable. An example SAS code has been provided in [Appendix I](#).

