## 4. ENDPOINTS

### 4.1 PRIMARY EFFICACY ENDPOINT

The primary efficacy endpoint is:

- ABR (spontaneous and total) during Part 2 when on final MarzAA dose level versus recorded historical ABR

Bleeding events will be evaluated as follows:

- Spontaneous versus traumatic/traumatic

A spontaneous bleeding episode is defined as one that is precipitated by normal ADL.

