### 7.5 HEMOPHILIA BLEED HISTORY

The frequency of hemophilia bleed history will be summarized descriptively for the prior 6 months and the prior 50 days respectively.

Individual plot to show the bleeding pattern will be presented for each subject by the time the bleeding starts and ends.

Hemophilia bleed history and other hemophilia history will be listed.

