### 8.1.2 Sensitivity Analyses

The analysis in [Section 8.1](#) will also be performed using the modified ITT population and per-protocol population.

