**Poisson regression model for primary sensitivity analysis:**

```
PROC GENMOD DATA = bleed;  
CLASS subjid time  
MODEL abr = time / DIST = poi LINK = log PRED;  
REPEATED SUBJECT = subjid/ CORRW TYPE = un;  
LSMEANS time/DIFF CL;  
RUN;
```

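### The SAP 8.1.1 model said to compare final-dose ABR with recorded history contains no history: it estimates mean ABR divided by 12, and its code treats annualized rates as bleed counts

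*SAP*

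**What the plan says.** The primary endpoint in SAP 4.1, matching Protocol 9.1, is "ABR (spontaneous and total) during Part 2 when on final MarzAA dose level versus recorded historical ABR".

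SAP 8.1.1 first sets out a one-sample exact Poisson test against a fixed rate of 12, one-sided at 2.5%, in the ITT population. It takes 12 from inclusion criterion 2 as the lowest ABR an eligible subject can have. A further paragraph then adds a PROC GENMOD Poisson model. Its stated purpose is "In order to compare ABR (spontaneous and total) during part 2 when on final MarzAA dose level with the actually recorded historical data"; its specification is ABR as outcome, with "intercept as the independent variable and log e transformed of 12 will be used as offset variable". That paragraph points to Appendix I for example code.

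Appendix I holds two Poisson programs:

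- The first, labelled for the primary endpoint, has "MODEL abr = / DIST = poi LINK = log PRED OFFSET = <ln (12)>" and an exact one-sided test of the intercept.
- The second, labelled for the primary sensitivity analysis, has "MODEL abr = time / DIST = poi LINK = log PRED" with "REPEATED SUBJECT = subjid/ CORRW TYPE = un" and least-squares-mean differences for time.

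SAP 8.1.2 says only that the 8.1 analysis "will also be performed using the modified ITT population and per-protocol population". Elsewhere, SAP 7.5 says of recorded history: "The frequency of hemophilia bleed history will be summarized descriptively for the prior 6 months and the prior 50 days respectively". SAP 8.2.1 compares pre- and post-treatment between-bleed intervals and proportions of bleeding days by paired t-test.

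**The concern.** The sentence and the model do not match. The sentence promises a comparison with what was recorded before the study; the model has nowhere to put that information. Its result would be reported as a comparison with history when it is a comparison with the constant 12.

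The ABR contrast that the endpoint names is then left to a program whose factor has no stated levels, whose history window is not given, and whose label does not match the section it should belong to. Those choices could be made after the data are seen.

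A second problem lies in the same code. Both programs use annualized ABR as the Poisson response. Over about 50 days one bleed becomes several annualized units, and the Poisson likelihood treats each unit as an observed event. Because the first program carries the primary-endpoint label, this reaches the test against 12 if the code is used as printed.

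**Working it through.** **1. The plan's own figure.** Inputs from SAP 3.5 and 8.1.1: null ABR 12, true ABR 6, one-sided 2.5%, n = 12 or 6. The critical value is the largest k with P(Poisson(12n) ≤ k) ≤ 0.025.

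- n = 12: mean 144, critical value 120, exact alpha 0.0227, power above 99.999%.
- n = 6: mean 72, critical value 55, alpha 0.0224, power 99.88%.

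Both stated powers reproduce, with one person-year per subject.

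**2. What the intercept-only model estimates.** With log E(ABR_i) = b0 + ln(12), the maximum-likelihood solution is exp(b0) = mean(ABR)/12. Testing b0 = 0 tests mean ABR = 12. History does not appear.

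**3. Illustration A (assumed data).** 12 subjects, 50 days each at final dose, 15 bleeds in total. By the SAP formula, months = 50/30.5 = 1.639, so one bleed contributes 12/1.639 = 7.32 to a subject's ABR. The ABRs sum to 15 × 7.32 = 109.8, mean 9.15.

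| Assumed mean recorded history | Model's exp(b0) | Ratio to history |
|---|---|---|
| 12 | 9.15/12 = 0.76 | 0.76 |
| 18 | 0.76 | 9.15/18 = 0.51 |
| 24 | 0.76 | 9.15/24 = 0.38 |

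**4. Inference from the first program, same data.**

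- ABR as the count: 109.8 against 144. P(Poisson(144) ≤ 109) = 0.0014 and P(Poisson(144) ≤ 110) = 0.0019, so p is about 0.001 to 0.002 depending on how the non-integer total is handled.
- Bleeds over exposure: 15 against 144 × 50/366 = 19.67. P(Poisson(19.67) ≤ 15) = 0.17.

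The estimate is the same (15/19.67 = 0.76); only the apparent precision differs. At a true ABR of 12, a 50-day ABR has variance 7.32² × 1.639 = 87.8, where the program assumes 12.

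Rejection rate at a true ABR of 12, 50 days each: rejection needs a total ABR of at most 120. Sixteen bleeds give 117.1 and seventeen give 124.4, so rejection means 16 bleeds or fewer. P(Poisson(19.67) ≤ 16) = 0.24, against a nominal 0.025.

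**5. Illustration B: the second program without an exposure offset (assumed data).** Take time as history versus final dose. Each subject has 9 bleeds in 183 days of history (ABR 18). Eleven subjects have 50 days and 14 bleeds in total; one has 10 days and 1 bleed (ABR 36.6).

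- As coded: mean ABR = (14 × 7.32 + 36.6)/12 = 11.59; ratio 11.59/18 = 0.64.
- Counts with a log(days) offset: 15 bleeds in 560 days, 15/(560/366) = 9.80; ratio 9.80/18 = 0.54.
- With equal exposure (12 × 50 days, 15 bleeds) both give 0.51.

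Here the consequence is weighting: ten days count as much as fifty. Short exposure is possible because the ITT set needs only one dose (SAP 5.3).

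**The case against.** **The comparator is settled as 12.** Protocol 9.1 calls 12 the historical control rate, and SAP 8.1.1 ties it to eligibility. This stands for the hypothesis test. A reader might infer that testing against 12 is itself improper because the endpoint names recorded history; the documents do not support that, since the fixed null is openly prespecified in both. It does not rescue the extra paragraph, which promises the recorded data and uses none.

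**Recorded history is used elsewhere.** True. A reader might infer that it is never used inferentially, which overstates the gap: SAP 8.2.1 has paired tests on intervals and bleeding days. What is missing is a contrast on the ABR scale.

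**The second program may be the intended contrast.** Possibly. Calling it uncited would go too far, because 8.1.1 points to Appendix I as a whole. But the model described there is the first program, and no text defines time or describes the second.

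**It is only example code.** The intercept-only form and ln(12) offset are in the body text, so the mislabelling does not depend on the appendix. The exposure fault in the second program does depend on uneven exposure: Illustration B is hypothetical, the documents give no rate of short exposure, and non-completers are replaced.

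**A historical ratio would be biased toward the drug.** This stands. Entry at a recorded ABR of at least 12 and escalation until free of spontaneous bleeds both push the ratio down. In simulated trials with no drug effect, a mean ABR of 12 before selection and a six-month entry window, the ratio averaged 0.78 if all subjects share one rate, and 0.82, 0.86 or 0.91 with between-subject CV of 0.3, 0.5 or 0.8. Nominal 2.5% one-sided tests rejected 12.8% down to 5.3% of the time. Escalation is left out of these figures. Any such ratio should therefore be supportive only.

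**Conclusion.** Wrong as written. The model in SAP 8.1.1 does not compare ABR with recorded history; this is algebra and needs no assumption. Nothing else in the documents supplies a defined ABR contrast with history.

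It is tempting to say that the model merely repeats the test against 12. That holds for the estimate only. As coded, its inference differs from an exposure-based test: p of about 0.001 to 0.002 against 0.17 in Illustration A, and about 24% rejection at a true ABR of 12. Those figures assume 12 subjects with 50 days each and Poisson bleeding; they shrink as exposure approaches a year, where the two tests coincide.

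The hypothesis of ABR below 12 is not in question. Eligible subjects should have recorded ABRs of at least 12, so the ratio to 12 does not exaggerate the reduction from history; it answers a different question.

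**What to change.** 1. In SAP 8.1.1, delete the claim that this model compares with recorded history and describe it as the test against the fixed rate of 12. Do not keep the first Appendix I program as coded: use the bleed count as response with offset log(12 × exposure in years), so that the test uses actual exposure.
2. In SAP 8.1.2, define the second program: bleed count as response, log(days observed) as offset, time as six-month recorded history versus Part 2 at final dose, clustered by subject. State one history length (SAP 8.2.1 already uses 180 days). Run it for total bleeds, and for spontaneous bleeds only if history is recorded by cause; Protocol 8.1 does not make that split clear.
3. Report the rate ratio with 95% CI as supportive only, beside the SAP 7.5 summaries. Note in words that entry selection and escalation both favour the drug and that an interval from about 12 clusters is approximate. Leave simulated bias figures out of the SAP, because their size depends on unknown heterogeneity. If the sponsor prefers no interval, paired descriptive ABRs (history and final dose) are the minimum.

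The cost is one reworded clause, a short paragraph and edits to two existing programs. Six-month history is already collected (Protocol 8.1), and no visit, dose or sample size changes. The price is a supportive ratio with a known direction of bias, and a test against 12 that is less often significant than the current code would suggest.

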### 8.1.2 Sensitivity Analyses

The analysis in [Section 8.1](#) will also be performed using the modified ITT population and per-protocol population.

## 8.2 SECONDARY ENDPOINTS AND ANALYSES

### 8.2.1 Analysis of Occurrence of Breakthrough Bleeds and Proportion of Bleeding Days

A breakthrough bleed is any spontaneous or traumatic bleed. Subjects who had breakthrough bleeds out of total bleedings will be summarized separately as spontaneous and traumatic as well as combined and listed using ITT, modified ITT population and per-protocol population.

Breakthrough bleeding events will be categorized and summarized as follows:

- Number and percentage of bleeds that are life threatening for each dose level within each study part
- Number and percentage that require hospitalization and/or blood transfusion for each dose level within each study part
- Number and percentage of muscle bleeds for each dose level within each study part

A listing of breakthrough bleeding events will be provided, including start and end date of bleeding.

Mean pre-treatment between bleeding intervals for all subjects will be compared with post-treatment between bleeding intervals for each dose level in Part 2 using paired t-test. This analysis will only be performed if there are at least 6 data points at pre- or post treatment. The analysis will be performed using ITT, modified ITT and per-protocol population.

The proportion of bleeding days pre-treatment by subject will be compared with the proportion of bleeding days post-treatment for each dose level in Part 2 using paired t-test after transforming the individual proportions by an arcsin transformation ( $2 \cdot \arcsin(\sqrt{p})$ ). This analysis will only be performed if there are at least 6 data points at pre- or post treatment. The proportion of bleeding days pre-treatment will be

